3. STUDY DESIGN

We will perform a Stage 2a⁴ two-arm RCT of MB-BP vs. enhanced usual care control. This is a pragmatic control group designed to inform physicians in well-resourced settings if MB-BP would be of service to refer patients to as compared to enhanced usual care patients. The study is intended to evaluate the impacts of MB-BP on the primary self-regulation outcome of interoceptive awareness (i.e. MAIA) as compared to an enhanced usual care group. Secondary self-regulation outcomes are described in the Objectives section outlined previously. This study also aims to evaluate the degree to which the engagement of MB-BP with self-regulation targets translates into improved prehypertension/hypertension medical regimen adherence, specifically for the Dietary Approaches to Stop Hypertension (DASH)-consistent diet.

The enhanced usual care control group was decided upon through recommendations by the Research Coordinating Center at Columbia University, the Data Safety Monitoring Board, and several collaborating cardiologists and family physician clinician-researchers. Enhanced usual care involves every participant being provided with a validated home blood pressure monitor (Omron, Model PB786N),¹⁷⁹ which has evidence in and of itself to potentially lower blood pressure, and is beyond usual care at this time.^{6,180} All participants who have Stage 2 hypertension (blood pressure $>140/90$ mmHg) will be offered to have their physicians notified, if not already being overseen for uncontrolled hypertension. For participants with uncontrolled hypertension who do not have a physician, we will work with participants to provide access within constraints of their health insurance. Enhanced usual care group participants receive an educational brochure from the American Heart Association entitled “Understanding and Controlling Your High Blood Pressure Brochure” (product code 50-1731).

All research assessments will take place in the Brown University Mindfulness and Cardiovascular Health Lab in Providence, RI. The MB-BP intervention classes will be offered in both a University and community-based setting.

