5. STUDY INTERVENTIONS

5.1 Interventions, Administration, and Duration

MB-BP Intervention Description: This study proposes to customize MBSR to participants with prehypertension/hypertension creating an intervention called Mindfulness Based Blood Pressure Reduction Study (MB-BP). Specifically, MB-BP is based on the standardized MBSR intervention described elsewhere,¹⁶¹⁻¹⁶⁴ and will consist of eight 2.5-hour weekly group sessions, a 2.5 hour orientation, and an 8-hour one-day session. MB-BP will be performed by qualified or certified MBSR instructors¹⁹⁰ with formal training in cardiovascular health (e.g. dietician, physician assistant, health and wellness coach, and those with an Associate's or Bachelor's degree in relevant health sciences), and further certification in MB-BP. MB-BP instructor training involves: (1) An initial 40 hour in-person or online videoconference training where the unique elements of MB-BP are introduced. (2) Two half-day in-person training retreats where MB-BP-specific teaching modules are practiced in peer groups, supervised by the senior MB-BP trainer, with peer and trainer feedback. (3) Studying specific evidence-based articles on hypertension etiology, treatment and prevention, as well as articles synthesizing evidence of mindfulness on hypertension and hypertension risk factors.^{10,183,191-193} A written exam evaluates knowledge in this area, for which instructors-in-training need to pass. (4) Supervised teaching of MB-BP in non-study participants is done using the Mindfulness-Based Intervention Teacher Assessment Criteria (MBI-TAC),^{1,2,194} and an annotated MB-BP Curriculum Guide until adequate quality is established within predefined criteria.

The unique areas of MB-BP are education on hypertension risk factors, hypertension health effects, and specific mindfulness modules focused on awareness of diet, physical activity, medication adherence, alcohol consumption, stress, and social support for behavior change. A Curriculum Guide has been created based on the standardized MBSR manual developed at UMass Medical School (**Appendix B**).^{163,164} MB-BP sessions contain instruction and practice in mindfulness meditation, and conversations about stress and coping. Students learn a range of mindfulness skills including body scan exercises, meditation and yoga. Homework consists of

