6.2.4 Randomization and Intervention Allocation

Randomization will occur following the completion of baseline assessments prior to the initiation of study intervention. Only individuals who complete the baseline assessments and indicate they are available for the upcoming courses will be included in the randomization process.

Stratified randomization will be used, as simple randomization can fail if it creates groups unbalanced for critical features known to affect outcomes.^{7,8} Stratified randomization can reduce both types I and II error, improve trial efficiency, and facilitate subgroup and interim analyses.⁷ Variables used to create strata include age (≤ 60 vs. > 60 years), gender (male vs. female), and/or uncontrolled hypertension (≥ 140 mmHg systolic pressure, or ≥ 90 mmHg diastolic pressure) vs. prehypertension (120 to < 140 mmHg systolic pressure, and 80 to < 90 mmHg diastolic pressure). Simple random sampling will occur within each of the eight strata, thus allowing for each arm of the study to be more balanced with respect to age, gender, and hypertension category. The total size of each stratum will vary from cohort to cohort. To conduct the randomization, a list of participant IDs and strata characteristics will be provided, and a trained researcher not affiliated with the study will perform the randomization on participants after baseline assessment and final determination of eligibility is complete. Randomization will be done using an online computer software program known as Research Randomizer (Version 4.0).⁹ The randomization process will occur after each new round of enrollment (i.e., unique cohort). If the cohort sample size is such that there are not enough participants for balance within the three strata, we will prioritize stratification by two key strata instead of three, specifically by baseline blood pressure status and gender. Furthermore, after randomization within strata, if sample sizes in the entire sample for cohort differ by more than one participant per group, then all imbalanced groups are re-randomized until the entire sample differs by no more than 1 participant per group (e.g. n=8 MB-BP, n=9 enhanced usual care control). Expected cohort sizes, consistent with the

SARP are 15-20 participants. We anticipate needing to run 6 to 7 cohorts to reach the target sample size.

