9. STATISTICAL CONSIDERATIONS

9.1 General Design

Analyses will evaluate (1) whether MB-BP influences self-regulation targets, (2) whether the MB-BP-induced changes in self-regulation targets are associated with changes in medical regimen adherence, and (3) whether MB-BP is associated with medical regimen adherence. Analyses will incorporate generalized linear models (GLM) with properly chosen link functions, performed using generalized estimating equations (GEE) with robust standard error estimators.^{245,246} This provides an extension of regression analysis to the case of correlated or repeated observations, allows for inclusion of both continuous and discrete dependent variables, and enables modeling of covariance structures when observations are correlated across time. Following “intention-to-treat” principles, analyses will be conducted on all participants in the randomized controlled trial, regardless of intervention completion. Analyses will use GLM with identity links for normally distributed data. The between-groups independent variable in the GEE analysis is intervention condition, with control conditions as distinct referent groups. Categorical variables will be included in GLM/GEE models as indicator variables with one level chosen as referent. Continuous independent variables such as age and baseline blood pressure would be included as linear terms. In addition, we will include assessment time as a linear term and possibly with an additional quadratic term to capture possible non-linear relationship of time with the outcomes. It is conceivable that one would observe a steeper slope in the initial months that would decrease in the pursuing months. Thus, the use of a quadratic term for assessment time would be able to capture these phenomena. To evaluate self-regulation targets as mediators of the effects of MB-BP on medical regimen adherence, mediation analyses described by Valeri and VanderWeele will be employed.²⁴⁷ Such analyses will allow for potential interactions between the exposure and mediator of interest and account for potential confounders of the exposure-mediator, mediator-outcome, and exposure-outcome relationships using standard regression techniques. These methods estimate total, indirect and direct effect sizes, as well as statistical variance.²⁴⁷

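### Section 9.1 names no GEE cluster and no class term; if participants are the clusters and MB-BP classmates are correlated, the MAIA between-arm interval is too narrow

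*Combined protocol and SAP*

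**What the plan says.** Section 5.1 describes MB-BP as a taught group programme that "will consist of eight 2.5-hour weekly group sessions, a 2.5 hour orientation, and an 8-hour one-day session". On the other side, Section 3 says "Enhanced usual care group participants receive an educational brochure from the American Heart Association". Every participant also gets a home blood pressure monitor, and no group sessions are described for controls. Grouping therefore arises in one arm only.

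Section 6.2.4 randomizes within cohorts of 15-20 and states: "We anticipate needing to run 6 to 7 cohorts to reach the target sample size". It does not say how many classes each cohort feeds. It asks only that participants "indicate they are available for the upcoming courses", and Section 3 adds: "The MB-BP intervention classes will be offered in both a University and community-based setting".

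Section 9.1 is the sole analysis text; Sections 9.3 and 9.6 refer back to it. It calls GEE an "extension of regression analysis to the case of correlated or repeated observations", and the only dependence it describes is over time: the method "enables modeling of covariance structures when observations are correlated across time". The terms it names are intervention condition, assessment time and covariates: "Continuous independent variables such as age and baseline blood pressure would be included as linear terms". Class, cohort and instructor do not appear.

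**The concern.** People taught together share an instructor, a venue and a group, so their MAIA scores after the course may be correlated. A robust standard error protects only against correlation inside the cluster it is given. If that cluster is the participant, repeated measures on one person are covered and correlation between classmates is not.

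Two parts of the plan might seem to cover it but do not. Age and baseline blood pressure as covariates explain differences between people, not a shared class effect. The sensitivity adjustment for instructor warmth and credibility in Section 10.3.3 uses participant ratings as covariates; it does not estimate class-level variance.

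The MAIA is the single primary outcome, so its interval carries the trial's main conclusion.

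**Working it through.** **1. Reproduce the plan's sample size (Section 9.2).** Difference 3.7; average SD (6.5 + 6.0)/2 = 6.25; d = 3.7/6.25 = 0.592, which the plan gives as 0.59. A two-sample t-test with independent observations, two-sided alpha 0.05 and power 0.80, needs 45.8, so 46 per group. At d = 0.59, 46 per group gives 79.9%. The figure reproduces with no allowance for class.

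**2. Inputs.** Planned enrolment is 50 per group and dropout 10-15% (Section 9.2), leaving 50 x 0.90 = 45 or 50 x 0.85 = 42.5 per group. There are 6-7 cohorts (Section 6.2.4). Assumed, because the documents do not give them: one class per cohort, and a class-specific ICC of 0.01 to 0.10, defined as the share of MB-BP-arm variance due to class.

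**3. Formula, clustering in one arm only.** Class size m = 45/7 = 6.43 or 45/6 = 7.5. MB-BP design effect DE = 1 + (m - 1) x ICC. True SE / reported SE = sqrt((1 + DE)/2). Actual two-sided type I error = 2 x (1 - Phi(1.96/ratio)).

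| ICC | DE, 7 / 6 classes | SE ratio | Type I error |
|---|---|---|---|
| 0.01 | 1.054 / 1.065 | 1.014 / 1.016 | 5.3% / 5.4% |
| 0.02 | 1.109 / 1.130 | 1.027 / 1.032 | 5.6% / 5.8% |
| 0.05 | 1.271 / 1.325 | 1.066 / 1.078 | 6.6% / 6.9% |
| 0.10 | 1.543 / 1.650 | 1.128 / 1.151 | 8.2% / 8.9% |

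Simulating the t-test (100,000 trials per setting) agrees: about 5.2-5.9% at ICC 0.01-0.02, 6.5-6.9% at 0.05 and 8.1-8.9% at 0.10.

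**4. Milder cases, simulated.** With two classes per cohort (12-14 classes), type I error is 5.7-5.9% at ICC 0.05. With 6-7 classes and an unmodelled cohort ICC of 0.05 shared by both arms, it is 6.1-6.6% at class ICC 0.05. Allocation is balanced within cohort, so the shared part cancels from the contrast.

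**5. One possible GEE.** Take a participant-clustered GEE on both follow-ups with baseline MAIA as a covariate, assuming correlations of 0.5 with baseline and 0.6 between follow-ups, and no shared cohort effect. Type I error is about 8.6-9.6% at ICC 0.05. At ICC 0 it is already 5.7-5.8%, which is small-sample bias of the robust standard error and not a class effect. Adjustment removes person-level noise but not the class effect, so the same ICC counts for more. The plan does not state this model.

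**6. Power on the plan's t-test, d = 0.59.** The noncentrality is 0.59 x sqrt(n/2)/ratio. With 45 and 42.5 per group and no clustering, power is 79% and 77%. At ICC 0.05 the ratio is 1.066-1.078 for 45 per group and 1.061-1.073 for 42.5, and power is about 71-74%.

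**The case against.** The strongest reply is that this is silence, not error. Section 9.1 speaks of correlated observations in general and never says that the participant is the cluster or that classmates are independent. That stands: a reader might infer that the plan assumes independent classmates, and the documents do not support that. The point is an under-specification. It still needs repair, because a class-level cluster, if that was meant, would be unsafe without a small-sample correction when there are only 6-7 classes.

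The second reply is that the size rests on two figures the documents lack. That also stands. At ICC 0.01-0.02 the effect is small, and more classes or a shared cohort effect reduce it further.

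The third concerns the model. A reader might take the 8.6-9.6% in step 5 as the error rate of the planned analysis. Section 9.1 does not name baseline MAIA as a covariate, and part of that excess exists with no clustering at all. A different reading, with baseline MAIA kept as an outcome and a group-by-linear-time contrast, gave 7.3-7.4% at ICC 0.05. Neither model is stated in the plan.

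Within-cohort randomization does not answer the point. It cancels an effect shared by both arms, not one confined to MB-BP classes.

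**Conclusion.** The point holds in conditional form. On the natural reading of Section 9.1, a positive class-specific ICC makes the MAIA between-arm standard error too small. On the t-test used for the sample size, the inflation is minor at ICC 0.01-0.02 and visible at 0.05-0.10. These figures assume 45 completers per arm, 6-7 classes, a class effect in the MB-BP arm only and no shared cohort effect.

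The documents do not show that the ICC is positive, nor that the primary analysis is invalid; a reader should infer neither.

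Separately from clustering, the stated 80% power is not reached on the plan's own t-test after its own dropout allowance. A baseline-adjusted repeated-measures analysis could have higher power.

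**What to change.** **Section 9.1.** State that the participant is the GEE cluster in the main model. This makes the plan explicit but corrects nothing by itself. Record class membership. Pre-specify for the MAIA a partially nested sensitivity analysis on the same follow-ups and covariates, with a class random effect in the MB-BP arm only and small-sample degrees of freedom. Report it beside the main result, and state in advance that a significant main result it does not support will be described as sensitive to class clustering. Do not use an uncorrected class-level sandwich estimator with 6-7 classes: in the t-test setting it rejected 7.2-8.2% under the null.

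**Section 9.2.** State the expected number of classes per cohort. Restate power on the plan's t-test as 77-79% after dropout without clustering, and about 71-74% at an assumed class ICC of 0.05. Note that a baseline-adjusted repeated-measures analysis could do better.

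**Cost.** This is wording, one recorded variable and one extra analysis; neither sample size nor conduct changes. The class variance from 6-7 classes will be imprecise. Power of the sensitivity analysis is somewhat lower: with 43-45 per arm, one follow-up and no baseline adjustment, it is 73-76% at ICC 0 and 66-70% at 0.05. It is conservative (type I error 3.4-4.0%) if both arms share a cohort ICC of 0.05.

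Adjusting for the stratification factors is a separate good-practice matter and does not address class clustering.

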There is one study site, Brown University, carrying out the Mindfulness-Based Blood Pressure Reduction (MB-BP) study protocol outlined in this document. The University of Massachusetts Medical School is conducting the fMRI Imaging study that will recruit and scan a subset of MB-BP study participants (see separate fMRI study protocol and related MOP for full detail).

PROTOCOL SUMMARY

Study Title

Mindfulness Based Blood Pressure Reduction: Stage 2a Randomized Controlled Trial

Objectives

1. **Impacts of MB-BP on Primary Self-Regulation Targets:** Identify the impacts of MB-BP vs. enhanced usual care on the primary self-regulation target, specifically an assay of self-related processes (MAIA), described in Table 1. We hypothesize that MB-BP will significantly improve the MAIA in directions of better self-regulation, compared to control.
 - a. Secondary analyses will evaluate impacts on secondary self-regulation targets including an assay of emotion regulation (DERS), and cognitive processes (SART), described in Table 1.
 - b. Exploratory analyses will evaluate engagement of MB-BP vs. enhanced usual care with triangulated self-regulation target assays described in **Table 1** such as emotion regulation and stress (Pittsburgh Stress Battery, Perceived Stress Scale), self-related processes (Heart Beat Detection Task, Interoceptive Awareness fMRI Task), and cognitive processes (Mindful Attention Awareness Scale). Measures such as the neuroimaging Interoceptive Awareness fMRI Task will replicate assays in the MINDFUL-PC study.
2. **Self-Regulation Targets as Mediators of MB-BP Effect on Medical Regimen Adherence and Health Behavior Change:** Evaluate the degree to which the engagement of MB-BP with self-regulation targets translates into improved prehypertension/hypertension medical regimen adherence, specifically for the Dietary Approaches to Stop Hypertension (DASH)-consistent diet. We hypothesize that MB-BP will increase the DASH diet score compared to control, in participants with low DASH diet adherence at baseline (DASH diet score <5.5), and that the self-regulation primary outcome in Aim 1 (i.e. MAIA) is a significant mediator.

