1. STUDY OBJECTIVES

1.1 Primary Objective

1. **Impacts of MB-BP on Primary Self-Regulation Targets:** Identify the impacts of MB-BP vs. enhanced usual care on the primary self-regulation target, specifically an assay of self-related processes (MAIA) described in Table 1. We hypothesize that MB-BP will significantly improve the MAIA in directions of better self-regulation, compared to control.
 - a. Secondary analyses will evaluate impacts on secondary self-regulation targets including an assay of emotion regulation (DERS), and cognitive processes (SART), described in Table 1.
 - b. Exploratory analyses will evaluate engagement of MB-BP vs. enhanced usual care with triangulated self-regulation target assays described in **Table 1** such as emotion regulation and stress (Pittsburgh Stress Battery, Perceived Stress Scale), self-related processes (Heart Beat Detection Task, Interoceptive Awareness fMRI Task), and cognitive processes (Mindful Attention Awareness Scale). Measures such as the neuroimaging Interoceptive Awareness fMRI Task will replicate assays in the MINDFUL-PC study.
2. **Self-Regulation Targets as Mediators of MB-BP Effect on Medical Regimen Adherence and Health Behavior Change:** Evaluate the degree to which the engagement of MB-BP with self-regulation targets translates into improved prehypertension/hypertension medical regimen adherence, specifically for the Dietary Approaches to Stop Hypertension (DASH)-consistent diet. We hypothesize that MB-BP will increase the DASH diet score compared to control, in participants with low DASH diet adherence at baseline (DASH diet score <5.5), and that the self-regulation primary outcomes in Aim 1 are significant mediators.
3. **Further develop an MB-BP therapist manual and training program, including procedures for training, supervising, and evaluating therapists.** The PI will implement training he receives from the University of Bangor in the United Kingdom in May 2018 to implement the Mindfulness-Based Interventions Teacher Assessment Criteria (MBI-TAC) for MB-BP instructors, which is the most respected quantitative and qualitative tool developed to provide feedback for enhancing MBI teacher effectiveness, and establishing teacher certification.¹⁻³

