9.2 Sample Size and Randomization

Treatment Assignment Procedures

Statistical Power:

Utilizing effect sizes and statistical variance from the Stage 1 MB-BP clinical trial showed an increase of MAIA from baseline of mean 22.6 (SD=6.5) to mean 26.3 (SD=6.0) at 6-month follow-up, demonstrating a 3.7 increase in MAIA score ($p < 0.001$). Power analyses using the T statistic and non-centrality parameter, with alpha (two-tailed) set at 0.05 and beta at 0.2, shows with a MAIA increase of 3.7 in MB-BP vs. control, sample size requirements are 46 per group. With DASH diet score increasing from 2.78 (SD=0.61) at baseline to 3.37 (SD=0.81) at 6-month follow-up in the Stage 1 MB-BP study in the 67% of participants with a low DASH score (< 5.5), demonstrating a DASH diet score increase of 0.59 ($p < 0.001$). Using an effect size of 0.5, power analyses using the T statistic and non-centrality parameter

suggest that, with alpha (two-tailed) set at 0.05 and beta at 0.2, a sample size of 33 per group will be sufficient.

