9.5.2 Secondary Outcomes

Self-regulation outcomes foster triangulation, including further validated measures of interoceptive awareness (Heartbeat Detection Task,^{250,251} Interoceptive Awareness fMRI Task²⁵²⁻²⁵⁴), stress and emotion regulation (Difficulties in Emotion Regulation Scale,²²¹ Pittsburgh Stress Battery,²⁵⁵⁻²⁵⁹ Perceived Stress Scale,^{219,220} Beck Anxiety Inventory,²⁰³⁻²⁰⁹ CESD-R^{201,202}), attention control (Sustained Attention to Response Task,²²⁸⁻²³³), self-compassion (Self-Compassion Scale Short Form¹²¹), and self-efficacy (Self control scale and SECD-6 Scale²⁶⁰⁻²⁶⁷).

Medical regimen adherence outcome: Diet, assessed utilizing Dietary Approaches to Stop Hypertension (DASH) eating pattern score,¹⁸¹ measured via diet history food frequency questionnaire.¹⁸² The measure assesses adherence to JNC-7 guidelines DASH eating pattern score (range 0-8).^{181,183}

Medical regimen adherence secondary outcomes: (1) *Alcohol consumption:* Amount and frequency of alcohol consumption, will be assessed via self-report utilizing standard questions from the behavioral Risk Factor Surveillance Survey.¹⁸⁴ AHA/ACC hypertension clinical practice guideline cut-point of healthy alcohol intake is ≤ 2 drinks (e.g. 24 oz. beer, 10 oz. wine, or 3 oz. 80-proof whiskey) per day in men and ≤ 1 drink per day in women.¹⁰ Medical regimen adherence will be defined as adherence to JNC-7-recommended behavioral and medication treatment of hypertension.¹⁸³ (2) *Electronically-Measured Antihypertensive Medication Adherence:* measured continuously using electronic medication bottle caps (eCAPS, Ottawa, Canada)¹⁸⁵ (3) *Body Mass Index:* height and weight directly assessed using standard epidemiologic methods, with change evaluated in participants considered overweight or obese ($BMI \geq 25 \text{ kg/m}^2$).¹⁸⁶ (4) *Physical activity:* We will use the International Physical Activity Questionnaire which has undergone substantial validity and reliability testing.¹⁸⁷⁻¹⁸⁹ Adherence to Joint National Commission-7 (JNC-7) guidelines is 30 min aerobic physical activity ≥ 4 days per week.¹⁸³

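### The DASH comparison has no single analysis population, and the stated 33 per group for 80% power applies only to participants with baseline DASH below 5.5

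*Combined protocol and SAP*

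**What the plan says.** **Where the DASH set is restricted.** Aim 2, in both the Protocol Summary and section 1.1, states the hypothesis "in participants with low DASH diet adherence at baseline (DASH diet score <5.5"). Section 9.2 sizes the comparison from Stage 1 data: "With DASH diet score increasing from 2.78 (SD=0.61) at baseline to 3.37 (SD=0.81) at 6-month follow-up", observed "in the 67% of participants with a low DASH score". It continues "Using an effect size of 0.5, power analyses using the T statistic and non-centrality parameter" and arrives at 33 per group at two-sided alpha 0.05 and 80% power. The mediation paragraph of 9.2 also counts only low-DASH participants, 107 of 160 across the UH2 and UH3 phases.

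**Where it is not.** Section 9.1 lists the effect of MB-BP on medical regimen adherence among the analyses. Under the intention-to-treat principle it then says "analyses will be conducted on all participants in the randomized controlled trial, regardless of intervention completion". Section 9.3 (Definition of Populations) and section 9.6 (Data Analyses) only refer back to 9.1. Section 9.5.2 gives "Medical regimen adherence outcome: Diet, assessed utilizing Dietary Approaches to Stop Hypertension (DASH) eating pattern score" with no baseline cut-off, and neither does section 3, which calls DASH the primary adherence outcome. The BMI entry in the same 9.5.2 list does state a subset: "with change evaluated in participants considered overweight or obese".

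**Other inputs.** The trial randomises 50 per arm. Section 9.2 assumes average dropout of 10-15%.

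**The concern.** The lead adherence outcome is hypothesised and sized in one population, while the sections that define populations and outcomes do not carry that population forward. An analyst who follows 9.3 to 9.1 and then to 9.5.2 could test DASH in all 100 participants. An analyst who follows 1.1 and 9.2 would test it in about 67.

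Two things are at stake. First, the power statement describes only one of the two analyses. Adding the roughly one third of participants at or above 5.5 changes both the average effect and the spread, in ways the plan does not quantify. Second, if the set is not fixed in advance, the choice between two defensible readings could be made after the data are seen.

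**Working it through.** **Inputs from section 9.2:** low-DASH SDs 0.61 (baseline) and 0.81 (6 months); effect 0.5; two-sided alpha 0.05; low-DASH share 67%; dropout 10-15%. **From sections 3 and 6.2.4:** 50 per arm. Power is from the two-sample noncentral t, the method that 9.2 names, with noncentrality (effect / SD) x sqrt(n/2) and 2n - 2 degrees of freedom.

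**1. Reproduce the plan's figure.**
- Pooled SD = sqrt((0.61² + 0.81²)/2) = 0.717.
- With 0.5 read as DASH points, d = 0.5/0.717 = 0.70. Normal approximation: n = 2 x (1.96 + 0.84)² x 0.717²/0.5² = 32.3, rounded up to 33. The noncentral t gives 79.7% power at 33 per group. The stated figure is reproduced.
- With 0.5 read as Cohen's d, about 63-64 per group would be needed. The stated 33 therefore matches only 0.5 DASH points.

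**2. Low-DASH set in this trial.** The expected number is 0.67 x 50 = 33.5 per arm.

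| Dropout | Low-DASH per arm | Power |
|---|---|---|
| 0% | 33.5 | 80.3% |
| 10% | 33.5 x 0.90 = 30.2 | 75.9% |
| 15% | 33.5 x 0.85 = 28.5 | 73.4% |

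Keeping 33 low-DASH completers per arm would take 33/(0.67 x 0.90) = 54.7 to 33/(0.67 x 0.85) = 57.9, or about 55-58 randomised per arm.

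**3. All participants, 50 per arm.** Average effect = 0.67 x 0.5 + 0.33 x (effect in those at or above 5.5). The documents give neither that effect nor a full-sample SD. The effect is varied below. The SD is held at 0.717, which assumes that adjusting for baseline DASH brings residual spread down to the low-DASH level.

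| Assumed effect at or above 5.5 | Average effect | Power, no dropout | Power, 10% / 15% dropout |
|---|---|---|---|
| 0 | 0.335 | 63.8% | 59.2% / 56.7% |
| 0.25 | 0.418 | 82.2% | 78.0% / 75.6% |
| 0.5 | 0.500 | 93.2% | 90.5% / 88.8% |

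At this SD and without dropout, reaching 80% needs an average effect of 0.406. That means (0.406 - 0.335)/0.33 = about 0.21 points in the high-DASH third.

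**The case against.** The best reply is that there is no contradiction, only a restriction not repeated. The 9.1 sentence is a general intention-to-treat statement about keeping non-completers. It does not mention DASH and is compatible with intention-to-treat within the baseline subgroup. Section 9.2 is itself part of section 9, and it names the low-DASH set both for sizing and for the mediation analyses. With the two statements of the objective, the cut-off is prespecified and visible. The BMI contrast is also imperfect: the alcohol and physical activity entries in 9.5.2 carry no subset either, although 9.2 discusses their mediation power in terms of non-adherent participants. MAIA, not DASH, is the sole primary outcome.

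Most of this stands. The mismatch arises by omission, and the low-DASH reading is the more natural one. What remains is that the section headed as the definition of populations leads only to all participants, and the outcome definition does not correct it. The plan does not settle which set carries the main DASH result.

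A reader might go further and infer that an all-participant analysis is certainly underpowered, perhaps severely so on raw follow-up scores with a wide full-sample SD. The documents do not support that. They give no effect, mean or SD for participants at or above 5.5, and a score of 5.5 on a 0-8 scale still leaves up to 2.5 points of room. Section 9.1 plans repeated-measures GEE, not a comparison of unadjusted follow-up scores. An SD built from the cut-off would be fragile too: 5.5 lies (5.5 - 2.78)/0.61 = about 4.5 SDs above the low-DASH baseline mean, so the cut-off and the means may not be on the same scale.

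**Conclusion.** The point holds as a gap in specification. Two sets can be read from the plan, about 67 or 100 participants before dropout, and the 33 per group supports only the smaller one. All-participant power cannot be fixed from the documents. Under the assumptions shown it runs from about 64% to 93% before dropout, so it may fall below or above 80%.

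The low-DASH set does not secure the stated power either. It gives about 80% only if nobody drops out, and 73-76% at the plan's own dropout rate. These figures assume that the Stage 1 SDs and the 67% share carry over, that low-DASH participants split evenly between arms, and that the two-sample t is a fair stand-in for the GEE. The MAIA analysis is unaffected.

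**What to change.** - **Sections 9.1, 9.3 and 9.5.2:** state that the MB-BP versus control DASH comparison is made in all randomised participants with pre-randomisation DASH below 5.5, regardless of intervention completion. Section 6.2.4 places randomisation after the baseline assessments, so the subgroup is fixed beforehand and the comparison remains a randomised one. The DASH entry in section 3 should match.
- **Same sections:** name the all-randomised DASH comparison, adjusted for baseline DASH, as supportive.
- **Section 9.2:** state that the effect size of 0.5 means 0.5 DASH points (d about 0.70). Restate power in the low-DASH set as about 80% with no dropout and about 73-76% after 10-15% dropout.

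The cost is wording, one supportive analysis and a slightly less favourable power statement. No new data are needed.
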